### Infant Exclusion criteria are:

- 1. Neonatal Abstinence Syndrome
- 2. Humidified incubator
- 3. Diaper rash
- 4. Pre-existing or genetic skin conditions
- 5. Severe illness requiring 1:1 nursing care: e.g. minimal stimulation protocol, high frequency ventilation, vasopressor drug support, or body cooling.

Infants will be recruited and enrolled as soon as they meet study criteria (**see Figure 1**. **Study Schemata**). Data collection will begin following study enrollment and will continue until 6 weeks following randomization (**see Table 1**).

Figure 1. Study Schemata

c. Intervention: Infants will be randomly assigned and stratified by birth weight (≤ 800 grams, >800 grams to 1150 grams, > 1150 grams) to either 3- or 6- hour bundled diaper care. All infants will receive bundled care per unit standards until they are eligible for 3-hour bundled care. Infants typically transition to 3-hour bundled care once they are receiving interval feedings every three hours. This transition usually occurs before 3 weeks chronological age in infants >800 grams at birth and by 6 weeks

for infants ≤ 800 grams. Other care activities included in the standard 3-hour bundle vary based upon infant treatment needs, but usually include a diaper change. The only difference in a 3-hour and 6-hour bundled care event will be the timing of the diaper change. Infants will receive a diaper change at either 3 or 6 hours. While 3-hour bundled care is standard of care, this is a clinical environment in which caregiving cannot be expected to occur exactly every three hours to the minute, therefore both expected and actual times for the bundled care events will be collected to include in data analysis as needed. Infants who are receiving the 6-hour bundled diaper care will continue to receive 3-hour care interventions for all other interventions or as dictated by infant care needs. At the 3-hour caregiving interval in which the 6-hour bundled care infants are not due for a diaper change, the nurse will peek into the diaper to ensure there are no stool present. If stool is present, a diaper change should occur and the deviation from the protocol noted in the bedside documentation.

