d. Procedures: A neonatal provider will give approval for participation in the study. Parents will be approached for consent after eligibility screening is completed (≤ 32 weeks gestation). The principal investigator is a clinical nurse specialist and nurse scientist who has been affiliated in the Intensive Care Nursery since 1993. Study personnel will explain the study, allow time for questions, have a parent sign the consent form, and a copy will be given to the parent. Parents will provide consent for their infant's participation in the study and will give permission for themselves to participate in an interview about the study, if selected. Five parents from each group will purposively selected to participate in an interview. Parents will be selected to include parents with infants < 1000 grams at birth and parents with infant ≥ 1000 grams at birth.

[figure not shown]
Following consent, the infant will be monitored until all inclusion and exclusion criteria are met. At that time randomized to an intervention group and data collection will be initiated. The intervention will continue for six weeks at which time collection of data will stop and bundled diapered care will resume according to unit protocol. If the infant no longer meets inclusion criteria the intervention will be discontinued and routine data collection will be discontinued. The exclusion criteria will be noted, e.g. use of diaper cream, and data collection regarding any new illness characteristics or treatments will continue. If an infant requires a diaper change due to a stool or other needed procedure this will be recorded on a bedside card.

Ten nurses will be recruited for participation in interviews around intervention acceptability at the end of the study.

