- vii. Neonatal Skin Condition Score (see Figure 2): The NSCS will be collected twice daily (day and night shift by staff nurses) while infants are participating in the study. The NSCS is a reliable and valid measure of skin condition (Lund & Osborne, 2004)

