#### 8. Risk/Benefit Assessment

Risks associated with the intervention and data collection will be minimal. All of the study interventions including a less frequent diaper change are considered acceptable standard of care. The skin condition will be monitored twice daily to identify any potential change in the skin of the diapered area and if the NSCS is  $\geq 5$  due to dryness, erythema or skin breakdown in the diapered are, the intervention will be discontinued, the infant's provider will be consulted regarding the need for treatment and the infant will be monitored until resolution of the problem. The infant stress associated with stimulation due to data collection should be minimal. Data collection processes for the biomarkers should not cause discomfort and handling will be kept to a minimum. However, all research staff will have neonatal experience and be trained in developmentally appropriated infant handling and positioning.

The small risk of loss of confidentiality will be reduced by assigning code numbers to the samples. The key linking the identity of the subject to the code number will be separately maintained in the Research Office, under lock and key.

There may be a direct benefit to the subjects participating in the study including less physiological stress during caregiving or improved skin health. However, actual benefits will not be clear until future larger studies are conducted. By improving our understanding of the relationship between bundled diaper care and infant health outcomes more targeted interventions may be developed for general health, development and skin care.

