## Aim 2. Evaluate differences in infant skin health between 3- and 6-hour bundled care diapering at two sites (buttocks and chest)?

# **RQ1**. Does skin transepidermal water loss (TEWL) differ over time and at the end of 6 weeks between 3- and 6-hour bundled care diapering on the buttocks and chest?

**Analysis:** The trajectories of TEWL measured across the 18 days of bundle care will be fitted using a linear mixed model with a random intercept. We will first determine the best trajectory fit for TEWL over the 18 days. Once we select an appropriate trend for the data a model similar to the one described for weight will be estimated. We will remove technology burden scores and add time varying covariates for time since last bath, urine output, stool pattern, and feeding type indicator.

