#### **RQ4. Skin Microbiota**

**Analysis:** [name] in Shallowater, TX will provide the microbiome sample analysis services to determine composition of skin microbiome by 16S rRNA pyrosequencing. Funding for the microbiome analyses will come directly from Kimberly Clark's budget. Pyrosequencing data will be analyzed with a workflow based on QIIME software. Data will be compiled and relative percentages of microbes will be determined for each individual sample. Data will also be compiled at each individual taxonomic level according to the NCBI taxonomy criteria. Significance differences in relative abundance of specific taxa between the intervention groups will be calculated using the Kruskal Wallis test.

To assess the extent to which taxonomic diversity at the family and genus level can be used to distinguish microbial communities associated with skin swab samples; Principal Component Analysis (PCoA) will be used. Rarefaction, Chaol, Ace and Shannon indexes will be performed on the data to evaluate if diversity and richness of populations are different among subjects within the different intervention and over time. Demographic and other clinical data will be evaluated for basic correlation with any observed microbiome changes.

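### Section 4d ends routine data collection when the intervention stops, so infants stopped for diaper rash or cream lose later Aim 2 skin data for a reason tied to the outcome

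*Combined protocol and SAP*

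**What the plan says.** **Stop rule (Section 4d, Procedures).** "If the infant no longer meets inclusion criteria the intervention will be discontinued and routine data collection will be discontinued". The sentence after it reads: "The exclusion criteria will be noted, e.g. use of diaper cream, and data collection regarding any new illness characteristics or treatments will continue". What carries on after a stop is therefore information on illness and treatment, not the skin schedule.

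**Eligibility (Sections 4b and 5).** None of the four inclusion criteria concerns skin. Diaper rash is on the exclusion list in both sections; diaper cream is not listed in either. The link from the stop rule to skin comes from the cream example read together with the rash exclusion.

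**Skin-score stop (Section 8, Risk/Benefit Assessment).** If the NSCS is 5 or more "due to dryness, erythema or skin breakdown in the diapered are, the intervention will be discontinued". The infant is then monitored until the problem resolves. Section 8 does not say whether scheduled TEWL, pH, NSCS and swabs go on.

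**Collection window.** Section 4b gives the general schedule: "Data collection will begin following study enrollment and will continue until 6 weeks following randomization". Section 4e is narrower for the skin score: "The NSCS will be collected twice daily (day and night shift by staff nurses) while infants are participating in the study".

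**Analysis (Section 10).** Aim 2 asks about differences over time and at the end of 6 weeks. For TEWL, "The trajectories of TEWL measured across the 18 days of bundle care will be fitted using a linear mixed model with a random intercept". NSCS and pH get repeated-measures generalized linear models whose form is chosen later. For the microbiota, "Significance differences in relative abundance of specific taxa between the intervention groups will be calculated using the Kruskal Wallis test"; the visit is not stated, and diversity indices are also to be evaluated over time. No part of Section 10 says how stopped infants are handled.

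**The concern.** Section 3 gives the reason for studying skin: to learn whether longer diapering intervals carry a skin cost. An infant who develops rash shows that cost, and the stop rule ends that infant's skin measurements from then on. If 6-hour diapering does harm skin, more 6-hour infants would be stopped, and those still measured at week 6 would tend to look healthier than the group randomised.

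Stops can still be counted by arm, because Section 4d has the reason noted. The skin values after a stop cannot be recovered later. What is at stake is whether the as-randomised comparison at 6 weeks can be made at all from the data collected.

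**Working it through.** The plan states no rash rate, stop rate, effect size or SD, so there is no figure of its own to reproduce. Everything below except the visit schedule and the 25 per arm is an assumption.

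**1. Visits lost by a stopped infant.** Table 1 schedules skin probes and swabs three times a week for 6 weeks: 3 × 6 = 18 visits. A stop at the end of week w loses 18 − 3w: 15, 12, 9 or 6 for w = 1 to 4. If the infant would have gone home at 4 weeks (the minimum expected stay in Section 4b), the rule costs 12 − 3w = 9, 6, 3 or 0, and no amendment recovers week 6.

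**2. Simple week-6 contrast among infants still measured.** Let a trigger index be normal with SD 1 and mean d higher in the 6-hour arm. Infants above a common cut-off c are stopped, and ρ is the correlation between trigger and week-6 outcome. With φ the normal density and p3, p6 the stop rates:

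observed difference = d − ρ × [φ(c−d)/(1−p6) − φ(c)/(1−p3)]

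Take d = 0.5 and p3 = 0.10. Then c = 1.2816 and p6 = 1 − Φ(0.7816) = 0.217. The bracket is 0.3755 − 0.1950 = 0.181.

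| 3-hour stopped | 6-hour stopped | ρ = 0 | ρ = 0.5 | ρ = 1 (extreme) |
|---|---|---|---|---|
| 5% | 12.6% | 0.50 | 0.44 | 0.37 |
| 10% | 21.7% | 0.50 | 0.41 | 0.32 |
| 20% | 36.6% | 0.50 | 0.38 | 0.26 |

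In the 10% row the bias is 0.09 to 0.18 SD for ρ of 0.5 to 1. The standard error with 25 measured per arm is √(2/25) = 0.28 SD.

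**3. Planned group-by-day slope.** A simulation used 18 visits; random intercept, random slope and residual SD 0.7 each; harm rising from 0 to 0.5 score units at week 6; and the cut-off set so that 10% of the 3-hour arm stop. About 17.5% of the 6-hour arm then stop. This is fewer than in step 2 because the harm builds up gradually and a stop can fall at any visit. A random-intercept linear model was fitted.

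- Against the no-stop truth of 0.50, the slope is 0.47 to 0.49 (2% to 6% low), or 0.44 to 0.45 (about 11% low) if the triggering reading is also lost. Across 5% to 20% of the 3-hour arm stopped, it is 1% to 18% low.
- Against the as-randomised slope, it is 3% to 11% low if skin does not recover after the stop, 6% to 13% high with half recovery, and 28% to 40% high with full instant recovery (an extreme). The sign depends on what happens after the stop, which the rule leaves unmeasured.

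**4. What as-randomised data would show.** If stopped infants in both arms return to the 3-hour mean, the difference is d(1−p6) − ρ[φ(c−d) − φ(c)]. At ρ = 0.5 this is 0.5 × 0.783 − 0.5 × (0.2939 − 0.1755) = 0.33 SD; at ρ = 1 it is 0.27 SD.

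**5. Amount of data kept by continuing.** Section 4b wants at least 25 per arm with complete data, so stopped infants come on top of those. Randomised: 25/0.90 = 27.8 and 25/0.783 = 31.9, together 59.7. Stopped: 59.7 − 50 = 9.7. If stops fall at the end of week 3 or 2, 9.7 × 9 = 87 or 9.7 × 12 = 117 visits are kept, of 59.7 × 18 ≈ 1,075 (8% to 11%).

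**The case against.** **The largest figures belong to an analysis that the plan does not specify.** This stands. The 0.41 and 0.32 SD results describe a contrast among infants still measured at week 6. The TEWL, NSCS and pH models use every visit before the stop, and the model they are built on takes the group-by-day term as its estimate of interest. The slope simulation speaks most directly to TEWL, since the NSCS and pH models are not yet chosen. The Kruskal Wallis test is more exposed because no repeated-measures structure is described for it. However, its visit is not stated, and the normal formula in step 2 was not derived for relative abundances.

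**Continuing collection can move the estimate further from 0.5.** This also stands: 0.33 against 0.41 SD in the same example. The two numbers answer different questions. Collecting the values keeps both the as-randomised and the on-intervention comparison possible; the current rule allows only the second.

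**Extra measurement falls on damaged skin.** Section 8 promises that "handling will be kept to a minimum", whereas TEWL means a probe held on the skin for at least a minute and the swab means four strokes on the buttocks. The fix therefore needs clinical discretion for the buttock site.

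**Other sections may already keep the data.** A reader might infer that infants stopped at NSCS 5 or more certainly lose their skin data. The documents do not say so: Section 8 stops only the intervention and adds monitoring, and the general window in Section 4b runs to 6 weeks. That route is unclear rather than lost. For rash and cream stops, Section 4d is the specific rule, and neither the general window nor the monitoring restores TEWL, pH or swabs.

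**Conclusion.** The concern holds for stops due to rash or cream, and the NSCS stop needs clarifying. As written, later skin data are missing for a reason tied to the Aim 2 outcome, Section 10 is silent on stopped infants, and the as-randomised comparison at 6 weeks cannot be estimated without untestable assumptions.

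The size is unknown. Under the assumed 10% and 21.7% stop rates and 0.5 SD harm, a simple week-6 contrast falls to about 0.41 SD (0.32 at the extreme correlation), a bias below one standard error. The planned slopes move by a few percent against the no-stop truth in the main case, with no fixed sign against the as-randomised slope.

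A reader might infer that all Aim 2 results will hide skin harm. The documents do not support that: they give no stop rate in either arm, and the models for three of the four skin outcomes use the data before the stop. The point still merits an amendment, because the study exists to supply estimates for a larger trial and the lost values cannot be recovered. The stopping thresholds are clinical choices and are not challenged.

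**What to change.** **Amend Sections 4d and 8.**
- After a stop for rash, cream or NSCS of 5 or more: continue staff-scored NSCS and chest measures on schedule to 6 weeks after randomisation while the infant is hospitalised. Continue buttock TEWL, pH and swabs unless the clinical team judges the skin unsuitable, for example because of breakdown.
- After a stop for severe illness or a humidified incubator: continue medical-record outcomes and NSCS, with probes and swabs only if the clinical team agrees.

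**Add to Section 10.** Analyse all randomised infants as randomised. Record stop date and reason. Flag readings taken after cream. Report skin-triggered stops by arm, as counts with confidence intervals, beside the skin results. Add a sensitivity analysis that leaves out post-stop values. Describe the stops rather than test them: with 25 per arm, a Fisher test of 10% against 21.7% has only about 11% power.

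**Cost.** Protocol wording, and about 10 infants staying on measures that are already scheduled; staff nurses already score the NSCS. There is some added handling. Post-stop values reflect later care and cream and may shrink the as-randomised difference, which is why the stops by arm must stand beside it.

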#### e. Data Collection Measures

Study data will include maternal and infant demographics and medical history extracted from the medical record to describe the sample and for needed covariate data, physiologic data (e.g. heart rate, respiratory rate, oxygen saturation), and biomarkers of skin health (pH, transepidermal water loss, NSCS, microbiome). See **Figure 2** below for the timeframe for the collection of physiologic data and contents and length of bundled care. **Table 1** for the constructs, measures, and timing and frequency of data collection.

Figure 2. Timeline

Data Collection Timeline for Bundled Care and Physiologic Data

i. Medical Record Data: Participant participation is documented in the electronic medical record and data extraction from the electronic medical record can be accessed through the Duke Health System EPIC or through a Virtual Pin Network. Flow sheets, lab results and provider notes will be reviewed for the required data.

**Table 1. Data Collection** 

Construct	Measure/	Variable	Time frame		
	Instrument				
	Descriptive data to describe the sample				
Maternal history	EMR 	Age, medical hx. of skin disease,	Enrollment		
Infant characteristics	EMR	GA  , birth weight, diagnoses, antibiotics, delivery mode, lab values as required to describe skin health (e.g. albumin, protein, bilirubin) All bundled care event time frames from study entry to study discharge (expected vs. actual bundled times) During bundled care—respiratory support, changes in support, FiO 2 changes, average Daily FiO 2 , caffeine	Enrollment, 3x/week, or as available		
	Aim 1. Infant	Health			
Bundled care	Observation, videotape & EMR	Specific interventions (e.g. suctioning, positioning, offering pacifier, diapering) Length of bundled care events Time between bundled care events	Observer 3x/week for the 3-hour diaper group and 4s/week for the 6-hour group to allow for one within group comparison; Videotaped 1x/week Daily; retrieved 3x/week		
Physiologic stability	GE monitor	1-minute values of heart rate, respiratory rate and oxygen saturation 15 minutes before and after each observed bundled care event	3x/week for the 3-hour diaper group and 4s/week for the 6-hour group to allow for one within group comparison		
	EMR	# bradycardia events daily	Daily; retrieved 3x/week		
	EMR	# apneic events daily	Daily retrieved 3x/week		
	EMR	# desaturation events daily	Daily retrieved 3x/week		
	EMR	Feeding tolerance (emesis, gastric residual volumeml, feeding interruptions)	Daily retrieved 3x/week		
Weight gain	EMR	Daily weight in grams	Daily retrieved 3x/week		
	Aim 1. Covariates				
Development	EMR	Postmenstrual age (PMA)			
Severity of illness	Technology Burden	Total Score 0-100	Retrieved 3x/week to coincide with observation		
	EMR	Time in minutes since the end of the last bundled event	With each observation		

	Aim 2. Skin Health (buttocks and chest)			
Acid mantle	рН	0.00 to 14.00.	3x/week with observation	
development				
Water loss	TEWL	TEWL 	3x/week with observation	
	Dermalab			
Skin status	NSCS⁴	NSCS-range 3-9	Twice daily retrieved	
			3x/week	
Microbiome		Microbiota pattern	3x/week with observation	
	Aim 2. Covariates			
	EMR	PMA		
	EMR	Delivery mode		
	EMR	Time since last bath	3x/week with observation	
	EMR	Daily urine output	3x/week with observation	
	EMR	Time in minutes since the last bundled event		
	EMR	Stool pattern (categorical)	3x/week with observation	
	EMR	Feeding type (formula vs. breast and route; enteral	3x/week with observation	
		vs. nipple)		
	Bedside	Diaper size and brand	3x/week with observation	
	checklist			
	Stool	Scavenged	1x/week as available	
	Aim 3. Feasibility			
Intervention	Interviews	Parent perceptions	End of infant data	
acceptability			collection;	
and feasibility		Provider perceptions	At study end	
•	Exploratory Health Outcomes			
Late onset	EMR	Presence or absence	Two weeks after end of the	
sepsis			study	
Urinary tract	EMR	Presence or absence	Two weeks after end of the	
infection			study	

<sup>1EMR=electronic medical record; GA=gestational age at birth; TEWL=transepidermal water loss; NSCS=neonatal skin condition score.

- ii. Physiologic measures: Heart rate, respiratory rate, and pulse oximetry will be measured continuously with a GE Cardiopulmonary monitor (standard monitor at DUH) with acquisition from the server, sent to the PI weekly for all enrolled subjects in a data secured zip file. 1-minute values for each 24-hour observation in which a bundled care data collection occurred will be extracted and the required time frames will be extracted for analysis.
- iii. Bundled Care: The content of bundled care will be determined through the observational coding of all caregiving activities during weekly observations (3 times/week for 3-hour diapered and 4 times/week for the 4-hour diapered intervention group; see intervention section above) and 12-hour videotaping (1 time per week for each group) of bundled care events. The length of time for each bundled care event will be operationally defined as beginning when the nurse's hands enter the incubator and will end when the nurse's hands leave the incubator following caregiving.
- iv. Microbiome: One microbiome sample will be taken from the buttocks immediately after the diaper is removed and before the skin is cleaned, if there is NO stool present. A second swab will be collected from the chest at the same time. The following procedure will be used for all microbiome samples. Needed supplies will include a tube of sterile solution of PBS + 0.1%Tween 20 and a Nova Biostorage FLOQ swab with cuvette.
  - a. Remove the swab from the package
  - b. Insert the tip of the swab into the sterile PBS + 0.1% Tween 20 solution until moistened.

- c. Before the buttocks is cleaned, swab the left and right buttocks with two back and forth strokes on each buttocks for a total of four strokes.
- d. Place the swab tip into the cuvette and bend at scored break point until the tip remains untouched in the cuvette
- e. Seal the cuvette, and label it with the subject number, site, visit number, date, time, initials of the individual taking the swab.
- f. Place swabs into a -20°C (±5°C) freezer and store until end of study.
- v. pH: The Extech PH100 meter will be used to measure skin pH in the range of 0.00 to 14.00. The small flat surface electrode provides a non-intrusive accurate measure of pH. The instrument's probe will be placed at the center of the test site (either chest or diaper) and measurements will be taken. Each measurement will be performed by holding the probe flush over the skin at the test site. The measurement is taken instantly and will be recorded into RedCap via iPad.
- vi. Trans Epidermal Water Loss: TEWL values will be collected using the Dermalab. We will use non-invasive skin probes to perform each assessment of transepidermal water loss (TEWL). TEWL will be measured using the DermaLab® TEWL probe (Cortex Technology, Hadsund, Dermark), which consists of an open probe with paired sensors placed at different distances from the skin. Humidity and temperature are measured in each sensor to calculate vapor pressure gradients. The difference between two vapor pressure gradient measures is representative of TEWL at that point on the skin (Grove, Grove, Zerwick, & Pierce, 1999). Environmental humidity levels will also be measured using the DermaLab® before obtaining the TEWL measures. The average humidity readings from the two sensors will be recorded as environmental humidity. Individual probe covers will be used for each infant to prevent any cross contamination between patients. Each measurement will be performed by holding the probe flush over the skin at the test site for at least sixty (60) seconds and the average value (in g/m2\*hr) will be recorded. Probe covers are used to prevent cross contamination between patients, in addition, the probe will be thoroughly cleaned with 70% ethanol prior to and between participants to minimize cross-contamination or microbial transmission. The ethanol will be allowed to air dry prior to use of the probe.
- vii. Neonatal Skin Condition Score (see Figure 2): The NSCS will be collected twice daily (day and night shift by staff nurses) while infants are participating in the study. The NSCS is a reliable and valid measure of skin condition (Lund & Osborne, 2004)

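### Environmental humidity is recorded with the TEWL measures but is neither a listed covariate nor a term in the TEWL model, which may cost precision

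*Combined protocol and SAP*

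**What the plan says.** Section 4e(vi) describes an open probe with paired sensors and says how the reading arises: "Humidity and temperature are measured in each sensor to calculate vapor pressure gradients". It then adds a separate ambient measurement: "Environmental humidity levels will also be measured using the DermaLab® before obtaining the TEWL measures", and "The average humidity readings from the two sensors will be recorded as environmental humidity".

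Table 1 schedules TEWL "3x/week with observation", and Section 4 says that data collection "will continue until 6 weeks following randomization". The Aim 2 covariate rows of Table 1 cover postmenstrual age (PMA), delivery mode, bathing, urine, time since the last bundled event, stool, feeding, and diaper size and brand. Humidity is not among them.

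Section 10, Aim 2 RQ1 sets out the analysis: "The trajectories of TEWL measured across the 18 days of bundle care will be fitted using a linear mixed model with a random intercept". The form is borrowed from Aim 1 RQ3: "Once we select an appropriate trend for the data a model similar to the one described for weight will be estimated". That weight model contains group, day, group by day, PMA and technology burden, and its estimate of interest is the group-by-day coefficient b3. For TEWL the authors drop technology burden and "add time varying covariates for time since last bath, urine output, stool pattern, and feeding type indicator". Section 10 does not mention humidity anywhere.

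**The concern.** The plan orders a measurement and gives it no analytic use. All the covariates in the TEWL model describe the infant or the care given; none describes the conditions under which the probe was read, although the protocol itself says that TEWL is calculated from humidity and temperature at an open probe.

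The random intercept takes up stable differences between infants, but not changes in conditions within an infant. Section 4a allows infants to move to stepdown units, including a nursery at another hospital, and to continue the intervention there. Surroundings can therefore change during the six weeks, which is the dimension along which b3 is estimated. If humidity affects the readings, that variation ends up in the residual.

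Two things are at stake. One is the precision of the TEWL contrast in a study of about 25 infants per arm. The other is the TEWL variance estimate: Section 4b gives estimation of values and variances, to inform a larger study, as the goal.

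**Working it through.** **1. Is humidity used anywhere?** Setting the three places side by side: it is recorded in Section 4e(vi), absent from the Aim 2 covariates in Table 1, and absent from Section 10. It is recorded and unused.

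**2. The plan's own figures.** Three occasions a week for six weeks is 3 × 6 = 18, which matches the 18 days in Section 10. The target of 25 per group (50 in total, Section 4b) cannot be reproduced, because no effect size, standard deviation (SD) or power is given for TEWL. For scale: with 25 per arm and two-sided alpha 0.05 (Section 10), a single-time comparison has 80% power at (1.960 + 0.842) × √(2/25) = 0.79 SD, and 42% power at 0.5 SD. Precision is not plentiful.

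**3. Effect on the group-by-day term.** Take a random-intercept model with independent residuals and 18 equally spaced occasions numbered 0 to 17. Then Sxx = 18 × (18² − 1)/12 = 484.5, and

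SE(b3) = σ × √(2/(25 × 484.5)) = 0.0129 σ per occasion,

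where σ is the within-infant residual SD. If humidity explains a share R² of that residual variance and is unrelated to arm and day, SE(b3) is multiplied by √(1 − R²). The documents give no R², so a range is assumed:

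| Assumed R² | SE multiplier | Power, if 80% without humidity | Equivalent n per arm, 25/(1 − R²) |
|---|---|---|---|
| 0 | 1.000 | 80% | 25.0 |
| 5% | 0.975 | 82% | 26.3 |
| 10% | 0.949 | 84% | 27.8 |
| 20% | 0.894 | 88% | 31.2 |
| 30% | 0.837 | 92% | 35.7 |

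**4. Simulation check.** Sixty simulated trials were run at each of two R² values, with 50 infants, 18 occasions, a between-infant SD of 1, a within-infant variance of 1, a true b3 of 0.02, and humidity independent of arm. The ratio of SEs with and without humidity was 0.949 at R² = 10% and 0.838 at R² = 30%, in line with the formula. The mean b3 without and with humidity was 0.0212 and 0.0216 at 10%, and 0.0194 and 0.0196 at 30%. Omission changed the spread and not the centre.

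**5. The end-of-six-weeks question.** For a contrast at one time point the between-infant variance remains, so the gain is smaller. With intraclass correlation ICC (also assumed), the total SD is multiplied by √(ICC + (1 − ICC)(1 − R²)). For ICC 0.3 to 0.7 and R² 10% to 30% this runs from 0.985 (ICC 0.7, R² 10%) to 0.889 (ICC 0.3, R² 30%).

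**6. The variance carried forward.** Relative to a humidity-adjusted analysis, the unadjusted within-infant variance is larger by 1/(1 − R²): 1/0.95 = 1.05 at 5% and 1/0.70 = 1.43 at 30%.

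**The case against.** The strongest reply is that nothing in the documents shows an effect of ambient humidity on these readings. Section 4e(vi) describes a differential measurement, in which TEWL comes from a difference between sensors at two distances from the skin. Differencing tends to remove an ambient level common to both. Excluding infants in humidified incubators removes an obvious extreme as well. This stands in part: the share explained could be zero, and then there is no gain. It does not show that the share is zero, and the authors thought humidity worth recording.

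A second reply is that the model is only a template, so humidity could be added later. It could, but nothing prespecifies it, and a covariate chosen after the data are seen is worth less.

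A third is that humidity is not alone. Delivery mode, time since the last bundled event, and diaper size and brand are listed as Aim 2 covariates in Table 1 and also fail to appear among the terms of the TEWL model. That is true and needs its own reconciliation; it does not settle what to do with humidity.

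Finally, adjustment is not wholly free. Section 4e(vi) does not say where the ambient reading is taken or whether the diaper is already open. If it were taken beside a newly opened diaper, wetness could differ by arm and the buttocks covariate could be affected by treatment. This is a possibility and not a documented fact, but it should be closed off before the term is added.

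**Conclusion.** The point holds as a modest loss of precision. A recorded measurement condition is left out of both the covariate list and the TEWL model. If it explains 5% to 30% of within-infant residual variance, using it would multiply the standard error of b3 by about 0.97 to 0.84, with less gain for a single-time contrast. If it explains none, there is no gain. The range is an assumption, and the formula also assumes independent residuals and humidity unrelated to arm and day. The variance carried to the larger study would be too large only relative to an analysis that adjusts for humidity.

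A reader might infer more than the documents support:

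- **Bias.** Omission does not bias the randomized group-by-day contrast in expectation. A chance imbalance in conditions is ordinary sampling error, and stable differences between rooms fall largely on the random intercept.
- **Established noise.** No passage says that humidity is a known source of error in these readings.
- **A humidity value for each TEWL reading.** The text says only that humidity is measured ahead of the TEWL measures; one value per reading is a reasonable inference, not a statement.
- **Lost data.** The values are kept and remain usable; they simply have no stated use.

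In an exploratory study with no TEWL power target, this is a low-priority improvement.

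**What to change.** In Section 10, Aim 2 RQ1, prespecify recorded environmental humidity, centred at its overall mean, as a time-varying covariate in the TEWL models for chest and buttocks. (The plan states separate models by site for pH; I take the same to be meant for TEWL.) Add it to the Aim 2 covariate rows of Table 1 with its timing. In Section 4e(vi), specify that it is the ambient reading taken before the diaper is opened, so that arm cannot affect it. Report the model without humidity as a sensitivity analysis, which also shows how much of the variance it explains and gives the larger study both variance estimates.

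The cost is a few lines of text and one extra parameter, against up to 50 × 18 = 900 readings per site with complete data. TEWL readings with missing humidity would drop out of the adjusted model; because the same instrument supplies both values, these should be few, and the model without humidity retains them. No new variable has to be collected.
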